### **12.4 Statistical Methods**

Sensitivity and specificity of the lollipop swabs will be calculated.

The primary variable is binary (positive or negative). A separate subgroup analysis of sensitivity/specificity of lollipop swabs will be calculated for asymptomatic, symptomatic (<7 days), and symptomatic (>7 days) individuals.

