Study Population	COVID-positive patients ages 4 and above admitted to a hospital in the Madison, Wisconsin metropolitan area.
Statistical Methodology	The results of the lollipop swab will be compared to that of the known positive NP PCR to estimate the performance of the lollipop test to diagnose COVID-19. Falsely negative lollipop samples will be compared with the corresponding NP sample for cycle threshold.
Estimated Subject Duration	The duration of the study for each subject is a single study visit that will take approximately 30 minutes.
Estimated Enrollment Period & Study Duration	Study enrollment will occur over 6 months with the total expected duration of the trial to be 12 months.

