## 6.0 STUDY OBJECTIVES AND ENDPOINTS

Objectives	Endpoints
Primary To determine the performance characteristics of oral lollipop swabs compared to NP swabs for diagnosing COVID-19 via PCR molecular testing.	Tabulated results from NP vs. lollipop swab-based PCR COVID-19 tests.
Secondary To identify clinical characteristics of patients when there are discordant results for NP and oral lollipop test results.	Correlation of clinical characteristics to participants with discordant test results

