## **12.0 STUDY ANALYSIS**

### **12.1 Statistical Hypotheses**

- Primary Efficacy Endpoint(s):**

- For participants who have had COVID-19 symptoms for <5 days, the sensitivity of lollipop swab-based PCR COVID-19 testing is non-inferior to the sensitivity of NP swab-based PCR COVID-19 testing.

- Secondary Efficacy Endpoint(s):**

- For participants who have had COVID-19 symptoms for  $\geq 5$  days, the sensitivity of lollipop swab-based PCR testing is inferior by 50% to the sensitivity of NP swab-based PCR COVID-19 testing.
- For participants who are asymptomatic, the sensitivity of lollipop swab-based PCR testing is inferior by 50% to the sensitivity of NP swab-based PCR COVID-19 testing.

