### **12.2 Sample Size Justification**

Based on a small pilot study in 2020-2021, sensitivity of lollipop swabs compared to NP was found to be 88%. As we will now be including both asymptomatic and symptomatic individuals, we anticipate the

sensitivity of the lollipop swab to drop to approximately 80%. With a Type I error rate of 5% and a power of 90%, our calculated sample size is 206.

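### Section 12.1 splits symptom duration at 5 days and section 12.4 at 7, with day 7 in no subgroup, so neither duration hypothesis, including the primary one, has a matching planned estimate

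*Combined protocol and SAP*

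**What the plan says.** Section 12.1 (Statistical Hypotheses) states three hypotheses, each for a different group.

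- Primary: "For participants who have had COVID-19 symptoms for <5 days, the sensitivity of lollipop swab-based PCR COVID-19 testing is non-inferior" to that of the NP swab.
- Secondary, symptoms for 5 days or more: "the sensitivity of lollipop swab-based PCR testing is inferior by 50% to the sensitivity of NP swab-based PCR COVID-19 testing".
- Secondary, asymptomatic participants: the same statement of inferiority by 50%.

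Section 12.4 (Statistical Methods) first plans sensitivity and specificity with no restriction on group. It then adds a subgroup analysis in which these quantities "will be calculated for asymptomatic, symptomatic (<7 days), and symptomatic (>7 days) individuals".

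Three other sections bear on which group is primary. The primary endpoint in section 6.0 is "Tabulated results from NP vs. lollipop swab-based PCR COVID-19 tests", with no mention of symptom duration. The synopsis (section 3.1) has the lollipop result "compared to that of the known positive NP PCR to estimate the performance of the lollipop test", again with no split. Section 12.2 says that in a pilot "sensitivity of lollipop swabs compared to NP was found to be 88" per cent. Because asymptomatic people are now included, it expects the "sensitivity of the lollipop swab to drop to approximately 80" per cent. It concludes: "With a Type I error rate of 5% and a power of 90%, our calculated sample size is 206".

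Section 7.1 lists duration of symptoms among the clinical information collected.

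**The concern.** The hypothesis section and the methods section should describe the same groups. Here they use different cut-points, and no passage reconciles them. An analyst who follows section 12.4 exactly would report four sensitivities (overall, asymptomatic, under 7 days, over 7 days), and none of them is for the group named in the primary hypothesis.

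What is at stake is which result answers the primary question. Three candidates are in writing: the under-5-day group (12.1), the under-7-day group (12.4) and the whole cohort (6.0, 3.1 and the opening of 12.4). The protocol itself expects these to differ, since it hypothesises non-inferiority before day 5 and inferiority by 50% from day 5. If the choice is still open when results are known, a reader cannot be sure that it was made independently of them.

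**Working it through.** **Step 1. Place each day of symptoms under both sections** (duration counted in whole days).

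| Symptom duration | Hypothesis in 12.1 | Subgroup in 12.4 |
|---|---|---|
| Days 0 to 4 | Primary (<5) | <7 days |
| Days 5 and 6 | Secondary (≥5) | <7 days |
| Day 7 | Secondary (≥5) | none |
| Day 8 onward | Secondary (≥5) | >7 days |
| No symptoms | Secondary (asymptomatic) | Asymptomatic |

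The under-7 subgroup mixes participants from two hypotheses. The over-7 subgroup omits days 5, 6 and 7 of the group it would have to represent. Day 7 is lost because the inequality is strict on both sides; those participants still count in the overall estimate. Only the asymptomatic hypothesis has a matching estimate.

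**Step 2. See which group the rest of the plan treats as primary.** The endpoint (6.0), the synopsis methodology (3.1) and the first sentence of 12.4 carry no duration restriction. Only section 12.1 puts the primary question in the under-5-day group.

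**Step 3. See which group the sample size describes.** Section 12.2 gives 88% (pilot), 80% (expected), 5% type I error, 90% power and a result of 206. It gives no formula, null value or sidedness. A one-sample comparison with null 88%, alternative 80% and two-sided 5% comes closest to the stated figure:

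n = [1.960 × √(0.88 × 0.12) + 1.2816 × √(0.80 × 0.20)]² / (0.88 − 0.80)²

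= [0.6369 + 0.5126]² / 0.0064 = 1.3215 / 0.0064 ≈ 206.5

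This match is inferred. Other readings of the same inputs give 172 (one-sided), 226 (null and alternative exchanged) and 440 per arm (two independent proportions, two-sided).

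The conclusion about power does not need the match. Section 12.2 itself explains the 80% by the inclusion of asymptomatic participants, so the calculation rests on a mixed-cohort sensitivity whatever formula was used. The 90% is therefore not shown to apply to the under-5-day group.

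**Step 4. Size of the effect on the estimates.** This would require sensitivity by symptom duration and the share of participants at days 5 to 7. The documents give no share. Their only statement about sensitivity by duration is the hypothesis itself. No figure follows from them.

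**The case against.** The strongest reply is that section 12.1 does fix the primary group in advance. Reporting under-7-day results as primary would visibly contradict it, and section 12.4 calls its split a separate subgroup analysis, which can be read as additional to the hypotheses. Duration is collected, so a table split at 5 days can be produced at any time. This stands in part. A reader might infer that the trial has no pre-specified primary group, or that the cut-point is free to be chosen afterwards; the documents do not support that, because under 5 days is written down in 12.1. But if the 12.4 subgroups are only additional, what remains of 12.4 is the whole-cohort estimate, which does not match the primary hypothesis either. The ambiguity remains.

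A second reply is that no non-inferiority margin or test is stated, so aligning the cut-points would still not allow the primary hypothesis to be concluded. That is true, and it is a separate gap. A margin, once stated, would still need a defined group to apply to.

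A third is that the strict inequality above 7 could be a symbol lost in PDF conversion. That is unlikely, since the greater-than-or-equal sign survives in sections 12.1 and 14.2. Even if it happened, only the day-7 gap would close; the conflict between 5 and 7 would remain.

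**Conclusion.** The point holds as a contradiction in the text. Sections 12.1 and 12.4 use different cut-points, day 7 has no subgroup, and neither duration hypothesis has a matching estimate in 12.4. The under-5-day primary hypothesis also conflicts with a whole-cohort endpoint and a sample size built on a mixed-cohort sensitivity. The harm is an ambiguous primary analysis group, which should be settled before results are examined.

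Two stronger conclusions are tempting. One is that the trial is underpowered for its primary hypothesis by a stated amount. The documents give neither the share of participants under 5 days nor a sensitivity or margin for that group, so they support only the statement that 90% power is not shown there. The other is that the mismatch would shift the estimate by a given number of points or reverse the conclusion. The inputs for that are missing too, and without a margin no reversal can be shown.

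The day-by-day mapping assumes duration in whole days. The reproduction of 206 assumes the one-sample formula, and the verdict does not depend on it.

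**What to change.** Make these changes in one amendment, before results are examined.

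1. Use one cut-point with exhaustive categories in both 12.1 and 12.4. The default that matches the stated hypotheses is asymptomatic, symptomatic <5 days and symptomatic ≥5 days. If 7 days was intended, write <7 and ≥7 in both sections.
2. State in 12.4 which stratum addresses which hypothesis, and label any other split exploratory.
3. State in 6.0 that the primary endpoint is evaluated in the early-symptom stratum.
4. State in 12.2 that the 206 and the 90% power rest on a mixed-cohort sensitivity and are not shown for that stratum. The sponsor should name the formula actually used; the one-sample match above is an inference and should not be written in as fact.

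If the sponsor prefers the whole cohort as primary, steps 3 and 4 are replaced by a rewrite of 12.1: it needs a new whole-cohort primary hypothesis, with the duration hypotheses made secondary. Section 12.1 contains no such hypothesis now, so this is a change to the stated primary question and not only a relabelling.

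The cost is a few sentences and no new data, since duration is already collected. Under the default route the price is a power statement less favourable than the present one. The missing margin and test need their own correction.

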### **12.5 Planned Interim Analysis**

An interim analysis will not be performed.

### **12.6 Handling of Missing Data**

Since the analyses of this study won't involve any formal multivariate or longitudinal statistical modeling, no imputation-based analyses will be conducted.

Guidelines promulgated in the National Research Council report on handling of missing data will be followed.

## **13.0 RISK/BENEFIT ASSESSMENT**

### **13.1 Known Potential Benefits to the Subjects**

There will be no direct health benefit to subjects.

### **13.2 Known Potential Risks**

#### **13.2.1 Known Interventional Risks**

There are no known or anticipated risks of the lollipop swab collection method. Our study team implemented a similar testing method in a previous study (2017-1425) and it was tolerated well by participants.

There is a risk of breach of confidentiality.

#### **13.2.2 Other Known Study Risks**

There are no known procedural risks potentially related to study participation.

### **13.3 Risk/Benefit Analysis**

The risks are minimal, and the potential benefit to society is significant.

## 14.0 DATA AND SAFETY MONITORING

### 14.1 Adverse Event (AE) Definition

Adverse event (AE) means any untoward medical occurrence associated with the use of an intervention in humans, whether or not considered intervention-related.

### 14.2 Serious Adverse Event (SAE) Definition

An adverse event is considered "serious" if, in the view of either the investigator or sponsor, it meets any of the following outcomes:

- Death
- A life-threatening adverse event
- Inpatient hospitalization or prolongation of existing hospitalization for ≥ 24 hours
- A persistent or significant incapacity or substantial disruption of the ability to conduct normal life functions.
- A congenital anomaly/birth defect.
- Important Medical Events (IME) that may not result in death, be life-threatening, or require hospitalization may be considered serious when, based upon medical judgment, they may jeopardize the patient or subject and may require medical or surgical intervention to prevent one of the outcomes listed in this definition (FDA, 21 CFR 312.32; ICH E2A and ICH E6).

### 14.3 Classification of an Adverse Event

#### 14.3.1 Severity of Event

All AEs will be assessed by the clinician using the Common Terminology Criteria for Adverse Events (CTCAE), version 5.0. For AEs not included in the protocol-defined grading system, the following guidelines will be used to describe severity.

Mild (Grade 1)	Events require minimal or no treatment and do not interfere with the subject's daily activities.
Moderate (Grade 2)	Events result in a low level of inconvenience or concern with the therapeutic measures. Moderate events may cause some interference with functioning.
Severe (Grade 3)	Events interrupt a subject's usual daily activity and may require systemic drug therapy or other treatment. Severe events are usually potentially life-threatening or incapacitating.
Life Threatening (Grade 4)	The subject was at risk of death at the time of the event.
Fatal (Grade 5)	The event caused death.

#### 14.3.2 Relationship to Study, Study Procedure(s) and/or Study Intervention(s)

For all collected AEs, the clinician who examines and evaluates the subject will determine the AE's causality based on temporal relationship and his/her clinical judgment. The degree of certainty about causality will be graded using the categories below.

Definitely Related	Clearly related to the study procedures/intervention and other possible contributing factors can be ruled out.
---------------------------	--

Probably Related	Likely related to the study procedures/intervention and the influence of other factors is unlikely.
Possibly Related	Possibly related to the study procedures/intervention and there are other factors that could be equally likely.
Unlikely to be related	Doubtfully related to the study procedures/intervention and there is another likely cause.
Unrelated	Clearly not related to the study procedures/intervention and/or evidence exists that the event is definitely related to another cause.

#### 14.3.3 Expectedness for Study, Study Procedure(s) and/or Study Intervention(s)

The PI will be responsible for determining whether an AE is expected or unexpected in relation to the study procedures and intervention(s) (as applicable).

An AE will be considered unexpected if the nature, severity, or frequency of the event is not consistent with the risk information previously described in the clinical protocol, device manual, investigator's brochure, the package insert(s), the IRB application, or the informed consent document. Expectedness is recorded for both study procedures and interventions.

#### 14.4 Time Period and Frequency for Event Assessment and Follow-Up

The occurrence of an AE or SAE may come to the attention of study personnel during study visits and interviews of a study subject presenting for medical care, or upon review by a study monitor. All AEs including local and systemic reactions not meeting the criteria for SAEs will be captured on the appropriate CRF. Information to be collected includes event description, time of onset, clinician's assessment of severity, relationship to study product (assessed only by those with the training and authority to make a diagnosis), and time of resolution/stabilization of the event. All AEs occurring while on study must be documented appropriately regardless of relationship. All AEs will be followed to adequate resolution.

Any medical condition that is present at the time that the subject is screened will be considered as baseline and not reported as an AE. However, if the study subject's condition deteriorates at any time during the study, it will be recorded as an AE.

Changes in the severity of an AE will be documented to allow an assessment of the duration of the event at each level of severity to be performed. AEs characterized as intermittent require documentation of onset and duration of each episode.

Events will be followed for outcome information until resolution, stabilization, or completion of study participation.

#### 14.5 Reporting AEs and SAEs

##### 14.5.1 Reporting AEs

- AEs will be recorded from enrollment until completing all study activities.
- AEs will be recorded regardless of whether or not they are considered related to the study device.
- All AEs will be recorded on the appropriate study specific REDCap Reportable Event form within the study's REDCap project.

##### 14.5.2 Reporting SAEs

The investigator will immediately report to the sponsor any SAE, whether or not considered study intervention-related, including those listed in the protocol or investigator's brochure and must include an

assessment of whether there is a reasonable possibility that the study intervention caused the event. Study endpoints that are SAEs (e.g., all-cause mortality) must be reported in accordance with the protocol unless there is evidence suggesting a causal relationship between the study intervention and the event (e.g., death from anaphylaxis). In that case, the investigator must immediately report the event to the IRB.

All SAEs will be followed until satisfactory resolution or until the site investigator deems the event to be chronic or the subject is stable.

## 14.6 Reporting of Pregnancy

Not applicable.

## 14.7 Unanticipated Problems

An unanticipated problem (UP), as defined by the DHHS Office for Human Research Protection (OHRP), is any incident, experience, or outcome that meets all of the following criteria:

- The incidence, experience, or outcome is unexpected given the research procedures described in protocol-related documents (e.g., the study protocol, the informed consent documents, the Investigator's Drug Brochure) and the characteristics of the subject population being studied. An event may be considered unexpected if it exceeds the nature, severity, or frequency described in the study-related documents, Investigator's Drug Brochure, product labeling, or package insert.
- The incidence, experience, or outcome is related or probably related to participation in the research study. "Probably related" means the incidence, experience, or outcome is more likely than not to be caused by the research study procedures.
- The occurrence of the incidence, experience, or outcome suggests that the research places subjects or others at a greater risk of harm (physical, psychological, economic, or social) than was previously known or recognized.

The investigator will report UPs to the reviewing IRB and to the Data Coordinating Center (DCC)/lead Principal Investigator (PI). The UP report will include the following information:

- Protocol identifying information: protocol title and number, PI's name, and the IRB project number;
- A detailed description of the event, incident, experience, or outcome;
- An explanation of the basis for determining that the event, incident, experience, or outcome represents an UP;
- A description of any changes to the protocol, informed consent documents, or other corrective actions that have been taken or are proposed in response to the UP.

Report UPs within the timeframe(s) specified by the IRB(s) of record.

## 14.8 Unanticipated Adverse Device Effect

An unanticipated adverse device effect (UADE) means any serious adverse effect on health or safety or any life-threatening problem or death caused by, or associated with, a device, if that effect, problem, or death was not previously identified in nature, severity, or degree of incidence in the investigational plan or application (including a supplementary plan or application), or any other unanticipated serious problem associated with a device that relates to the rights, safety, or welfare of subjects (21 CFR 812.3(s)).

An investigator shall submit to the sponsor and to the reviewing Institutional Review Board (IRB) a report of any UADE occurring during an investigation as soon as possible, but in no event later than 10 working days after the investigator first learns of the effect (21 CFR 812.150(a)(1)).

A sponsor who conducts an evaluation of an UADE shall report the results of such evaluation to the FDA and to all reviewing IRBs and participating investigators within 10 working days after the sponsor first receives notice of the effect. Thereafter the sponsor shall submit such additional reports concerning the effect as FDA requests (21 CFR 812.150(b)(1).]

#### **14.9      Incidental Findings**

Not applicable.

#### **14.10     Safety Oversight**

Safety oversight will be under the direction of the Principal Investigator.

#### **14.11     Study Monitoring**

Not applicable.

#### **14.12     Study Stopping Rules**

This study may be temporarily suspended or prematurely terminated if there is sufficient reasonable cause. Written notification, documenting the reason for study suspension or termination, will be provided by the suspending or terminating party to investigator and regulatory authorities. If the study is prematurely terminated or suspended, the PI will promptly inform the IRB and will provide the reason(s) for the termination or suspension.

Circumstances that may warrant termination or suspension include, but are not limited to:

- Determination of unexpected, significant, or unacceptable risk to subjects
- Demonstration of efficacy that would warrant stopping
- Insufficient compliance to protocol requirements
- Data that are not sufficiently complete and/or evaluable
- Determination of futility

Study may resume once concerns about safety, protocol compliance, and/or data quality are addressed and satisfy the applicable federal and institutional regulatory authorities.

### **15.0     STUDY FEASIBILITY**

#### **15.1     Economic Burden to Subjects**

Subjects will not have to pay for study procedures (such as home blood pressure monitors, 24-hour monitoring). The subject will not be billed by the healthcare system or their health insurance company for any costs related to a study procedure.

Subjects will be responsible for any costs related to their COVID-19 follow-up as directed by their healthcare team, such as clinic visits and medication, including all out-of-pocket costs.

#### **15.2     Facilities and Locations**

UW Health Kids American Family Children's Hospital and UW Health University Hospital inpatient units.

### **15.3 Feasibility of Recruiting the Required Number of Subjects**

While COVID levels fluctuate in the community, in 2023 at University Hospital/AFCH there are generally 10-20 individuals hospitalized with a positive COVID test on any given day. If the COVID rates are maintained, then obtaining the sample size is possible over the next few months.

If UW/AFCH stops pre-procedural or COVID admission screening, then the amount of known COVID-positive individuals will likely decrease and it may take a longer time to identify 225.

